4.2.3. Post Treatment Follow-up (FU) Period

Patients will be followed for safety and efficacy evaluations post treatment at Week 1, Week 6 and Week 12. Details are provided in [Table 3](#) and [Section 7.6](#).

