6. TREATMENT OF PATIENTS

6.1. Study Treatment

ClariVein RES is the endovenous administration of STS injection (1% and 3%) mechanically delivered as intravenous infusion via the ClariVein for the treatment of venous insufficiency associated with incompetent saphenous vein due to superficial venous reflux.

This study is limited to the treatment of one incompetent saphenous vein per treatment procedure. Refer to [Appendix C](#) VICARES Clinical Study Procedure Manual for detailed on the treatment procedure including ultrasound measurements and calculation of the STS volume required for administration.

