7.7.1. Discontinuation of Study Treatment/Procedure

Patients may voluntarily discontinue from the study for any reason at any time. If a patient decides to discontinue from the study, the Investigator will make every effort (e.g. telephone, e-mail, letter) to determine the primary reason for this decision and record this information in the patient's chart and on the appropriate CRF pages. A patient may be considered withdrawn if the patient states an intention to withdraw, fails to return for study visits, or becomes lost to follow-up for any other reason.

The Investigator should discontinue the study procedure for a given patient if, he/she believes that continuation would be detrimental to the patient's well-being.

Study treatment may be discontinued if any of the following occur:

- Adverse event
- Physician's decision
- Patient/guardian decision
- Protocol deviation
- Technical problems

Patients must be discontinued if any of the following occur:

- At the time, a patient discontinues from the study, a visit should be scheduled as soon as possible, or no later than within 14 days of the decision to permanently discontinue from the study.
- If the decision to withdraw the patient occurs on Day of Treatment (Visit 3) following the initiation of the treatment procedure and the patient is determined to be evaluable as defined in [Section 6.1](#), the patient should be followed up for safety and efficacy at Week 1, Week 6 and Week 12.
- If the decision to withdraw the patient occurs on Day of Treatment (Visit 3) following the initiation of the treatment procedure and the patient is determined to not be evaluable as defined in [Section 6.1](#), that patient should be followed up for safety at Week 1.

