10.13. Monitoring and Recording of Adverse Events

AE data collection will begin after a patient signs the ICF and will continue until completion of their Week 12 post-treatment follow-up visit (Visit 6). Any AE or SAE having an onset after the completion of Visit 6 (end of the study visit) will not be collected or reported unless the Investigator feels that the event may be related to the study drug.

Patients will be instructed by the Investigator or designee to report the occurrence of any AE. All volunteered, elicited, and observed AEs are to be recorded on the AE eCRFs.

The Investigator will assess all AEs regarding any causal relationship to the study drug ([Section 10.11](#)), the intensity (severity) of the event, action taken, and patient outcome.

The following criteria will be used to guide the assessment of intensity (severity):

- **Mild:** An adverse event that is asymptomatic or barely noticeable to the patient; not interfering with patient's daily activity performance or functioning; generally, not requiring alteration or cessation of study drug administration; and/or ordinarily not needing therapeutic intervention
- **Moderate:** An adverse event of sufficient severity as to possibly make the patient moderately uncomfortable; some interference with the patient's daily activity performance or functioning; generally, not impairing the patient's ability to continue in the study; and/or possibly needing therapeutic intervention.
- **Severe:** An adverse event generally causing severe discomfort; major interference with the patient's daily activity performance or functioning; generally requiring alteration or cessation of study drug administration; life-threatening; resulting in

significant disability or incapacity; and/or generally requiring therapeutic intervention.

All AEs will be followed until resolution, until deemed stable by the Investigator, or until the patient is deemed by the Investigator to be lost to follow-up.

For clinical study safety reporting purposes, the most recent version of the Investigator's Brochure (IB) will be used as the reference document to designate event expectedness. An AE is considered unexpected if the AE is not listed in the current IB or is not listed in the IB at the specificity or severity observed.

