11.2. Analysis Populations

11.2.1. Safety Population

The safety population will include all patients who are treated with ClariVein RES. Patients will be analyzed per the treatment they received.

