11.9. Analysis of the Safety Endpoints

Safety will be assessed based on adverse events (including selected events of interest), clinical laboratory tests, physical examination, vital signs, and concomitant medications. Safety data will be summarized by treatment group and overall. No statistical testing will be performed for safety data.

AEs will be coded using Medical Dictionary for Regulatory Activities (MedDRA). Treatment-emergent events are those adverse events that begin or worsen after initiation of the treatment procedure. The number and percentage of patients reporting treatment-emergent adverse events will be summarized by MedDRA System Organ Class (SOC) and Preferred Term. Treatment-emergent adverse events will be further summarized by severity and relationship to the treatment procedure.

Physical examination data will be listed per patient. No summaries will be provided.

Vitals signs data will be summarized by descriptive statistics for baseline, each post-treatment visit, and the change from baseline to each post-treatment visit.

All prior and concomitant medications will be coded using the World Health Organization Drug Dictionary. Concomitant medications are medications taken on or after the treatment day, regardless of when they were started. Prior medications are medications taken before the treatment day, regardless of when they ended. The number and percentage of patients using

concomitant medications will be summarized by Anatomical Therapeutic Chemical (ATC) 3 classification and preferred name.

Overall safety assessment will include evaluation of the following specific events:

- Neurological events including: stroke, TIA, visual symptoms, migraines
- Venous Thromboembolic Events (VTE) in the treated leg
- Post-treatment local effects including hyperpigmentation, granuloma formation, ulceration in the treated leg
- Thrombus formation in deep veins (e.g., femoral vein) in the treated leg
- Post-ablation superficial thrombus extension (PASTE) in the treated leg
- Local and systemic allergic reactions, including anaphylaxis

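### Section 7.7.1 names only a Week 1 safety visit for patients stopped mid-procedure and called not evaluable, an undefined term, while other sections run to Week 12; the Section 11.9 percentages would count unobserved late events as absent.

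*Combined protocol and SAP*

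**What the plan says.** Section 7.7.1 deals with patients withdrawn on the Day of Treatment after the procedure has begun, and splits them in two. If evaluable, "the patient should be followed up for safety and efficacy at Week 1, Week 6 and Week 12". If "the patient is determined to not be evaluable as defined in" Section 6.1, then "that patient should be followed up for safety at Week 1". No later visit is named for the second group.

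Section 6.1 describes the product and its administration, and adds: "This study is limited to the treatment of one incompetent saphenous vein per treatment procedure". It contains no rule on evaluability.

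Other sections make no exception for this group:

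- Section 4.2.3: "Patients will be followed for safety and efficacy evaluations post treatment at Week 1, Week 6 and Week 12".
- Section 7.7: a patient's study ends at the Week 12 visit, on withdrawal of consent, or on loss to follow-up. Being not evaluable is not listed.
- Section 10.13: adverse event collection starts at consent and "will continue until completion of their Week 12 post-treatment follow-up visit (Visit 6").

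On analysis, Section 11.2.1 states: "The safety population will include all patients who are treated with ClariVein RES". Section 11.9 states: "Treatment-emergent events are those adverse events that begin or worsen after initiation of the treatment procedure". It then reports the number and percentage of patients with such events, by group and overall. Section 11.1 says that missing safety data are not imputed.

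**The concern.** A patient whose procedure is stopped part-way has had the vein instrumented and may have received some STS. Whether that patient is scheduled for one safety visit or three depends on a label that the protocol does not define. Two sites could handle the same patient differently, and each could point to protocol text in support.

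The consequence reaches the safety tables. A treated patient last seen at about Day 7 remains in the denominator. Later thrombus, PASTE, hyperpigmentation, granuloma or ulceration, all named as events of interest in Sections 8.1 and 11.9, cannot be found at visits that do not take place. With no imputation and no adjustment for time observed, not looked for is tabulated as not present, and the late-event percentages are biased downwards. Section 11.6 says that the sample size rests partly on safety, so these percentages are among the trial's intended results.

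**Working it through.** **Plan's own figures.** The documents give no figure for stopped procedures or late-event rates. Their one relevant calculation, at least 99% power in Section 11.6, reproduces: 5.44/3.52 = 1.545, and a two-sided one-sample t-test at 0.05 with n = 25 has power above 0.9999. This point does not affect it.

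**Which clauses apply to a stopped, not evaluable patient who received STS?**

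| Question | Section | Answer |
|---|---|---|
| Safety visits named | 7.7.1 | Week 1 |
| Scheduled follow-up | 4.2.3 | Weeks 1, 6, 12 |
| Adverse event collection | 10.13 | to Week 12 |
| End of study | 7.7 | Week 12, consent withdrawn, or lost |
| Ongoing adverse events | 9.2, 10.13 | followed to resolution or stability; 10.13 also ends at loss to follow-up |
| In safety population | 11.2.1 | yes |

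The general discontinuation visit in Section 7.7.1, due within 14 days of the decision, does not reach Week 6 either. What is lost is therefore detection of new-onset events after Week 1, and the Week 6 and Week 12 ultrasound, hematology, coagulation and vital signs in Table 3. D-dimer at those two visits is conditional on the level exceeding Baseline, so it is not always lost.

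**Scheduled observation per affected patient.** From Table 3, Week 1 is Day 7 (±2) and Week 12 is Day 84.

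- 7/84 = 8.3% of the window (5/84 = 6.0% to 9/84 = 10.7%).
- 84 − 7 = 77 days and two of three visits are not scheduled.

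**Per arm.** Let k be the number of affected patients in an arm of 25; k is assumed. Planned days are 25 × 84 = 2,100, and the share lost is 77k/2,100. If late events occur at rate p and none is detected in unobserved patients, the expected crude percentage is p(25 − k)/25. The chance of seeing at least one late event is 1 − (1 − p)^(25 − k). The last two columns assume p = 5%.

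| k | Days lost | Expected crude % | P(at least one seen) |
|---|---|---|---|
| 0 | 0 | 5.0 | 0.723 |
| 1 | 3.7% | 4.8 | 0.708 |
| 2 | 7.3% | 4.6 | 0.693 |
| 3 | 11.0% | 4.4 | 0.676 |
| 5 | 18.3% | 4.0 | 0.642 |

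Across assumed p from 2% to 10%, going from k = 0 to k = 5 moves the chance of seeing an event from 0.397 to 0.332 (p = 2%) and from 0.928 to 0.878 (p = 10%).

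**One missed event.** If a single late event goes undetected, 1/25 = 4% (Wilson 95% interval 0.7% to 19.5%) is reported as 0/25 = 0% (0% to 13.3%). The intervals are added here for scale; Section 11.9 plans none.

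**The case against.** The strongest reply is that the two rules govern different things. Section 10.13 sets a collection window and Section 7.7.1 sets a visit. The bullet does not say that Week 1 is the only contact, volunteered events could still be recorded, and Section 10.14 requires serious events to be reported to the end of the study. That stands as far as it goes. It does not replace scheduled scans and laboratory tests, which are how a silent thrombus would be found.

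A second reply is that some of these patients may not be in the denominator. The Procedure Manual, Section 4.1.4.4, has the wire rotate over the first 1 cm without infusion, so a procedure can be initiated and stopped before any STS is given. Such a patient may fall outside the safety population. This also stands, and the point is limited to patients who received STS. Nor can one say that *evaluable* is an efficacy term; undefined, it could refer to exposure.

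A reader might go further and infer that patients stopped for toxicity are the ones observed least. The documents do not support that. The split is by evaluability, not by reason for stopping: a patient stopped for toxicity but evaluable is followed to Week 12, and stops for technical problems, deviations or patient choice fall under the same bullets. The event that caused the stop is followed to resolution or stability (Sections 9.2 and 10.13). After withdrawal of consent, Section 7.7.2 allows no further assessments, which is less observation still.

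**Conclusion.** The inconsistency is real and worth correcting. One clause gives a subset of patients a single safety visit, three others run to Week 12 without exception, and the term that decides between them is undefined. For a patient who received STS, scheduled safety observation falls to about 8% of the planned window while the patient remains in the denominator.

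The effect on the tables depends on an unknown count. With one affected patient in an arm it is slight; with five, the expected late-event percentage is a fifth too low. This rests on reading the Section 11.9 denominator as the safety population, since no other is named, and on late events in unobserved patients going undetected. Volunteered reports would reduce the shortfall.

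A reader might also infer that the rule conceals a safety difference between 1% and 3% STS. That would require stopping, or the not evaluable label, to differ by arm. The documents give no basis for assuming so, and Section 11.9 plans no safety testing. It remains a possibility, not a finding.

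**What to change.** Reconcile Sections 4.2.3, 6.1, 7.7, 7.7.1, 10.13, 11.2.1 and 11.9 so that one stated safety data-collection window applies to each patient in the safety population. Which follow-up schedule prevails is for the sponsor to decide; this review does not choose. Either define *evaluable* where Section 7.7.1 says it is defined, or stop using it to determine how long safety is observed. State in Section 11.2.1 whether a patient whose procedure was initiated but who received no STS counts as treated.

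If windows remain unequal, Section 11.9 should report events with onset after Week 1 over the patients actually observed to the relevant visit, by arm, with the number not observed. For example, with one late event and three patients unobserved, it would show 1/22 = 4.5% alongside the crude 1/25 = 4.0%.

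The cost is a short text edit and a little extra tabulation. Depending on how the sponsor reconciles the passages, it may also mean up to two visits already in the schedule for a few patients. No sample-size or power figure changes.

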7.7.2. Withdrawal of Consent

Patients may voluntarily withdraw consent to participate in the study for any reason at any time. Withdrawal of consent occurs only when a patient does not want to participate in the study any longer, does not want to have any further visits or assessments and does not want any further study related contact.

The Sponsor will continue to retain and use all research results that have already been collected for the study evaluation.

If a patient withdraws consent, the Investigator will make every reasonable effort (telephone, e-mail, letter) to determine the primary reason for this decision and record this information.

No further assessments will be conducted.

8. ASSESSMENT TYPES

8.1. Safety and Tolerability

Safety assessment will include overall evaluation of safety of ClariVein RES. Safety will be assessed based on:

- Adverse events
 - Type, incidence, severity (mild, moderate, severe), timing, seriousness, relatedness, outcome, action taken with study product, and treatment will be assessed and documented by the Investigator throughout the study
 - All spontaneous AEs will be monitored, processed, and reported per Sponsor's Standard Operating Procedure for handling AEs
- Vital signs (i.e., oral temperature, respiratory rate, heart rate and blood pressure)
- Clinical laboratory assessments
 - Hematological Assessment:
 - hemolysis
 - hematocrit,
 - reticulocyte count,
 - haptoglobins,
 - Intravascular Coagulation Assessment
 - plasma fibrinogen level
 - plasma D-dimer level platelet count
 - PT – prothrombin time
 - PTT – partial thromboplastin time

In addition, safety assessment will include evaluation of the following specific events:

- Allergic reactions, including anaphylaxis
- Neurological events including: stroke, TIA, visual symptoms, migraines
- Venous Thromboembolic Events (VTE) in the treated leg
- Post-treatment local effects including hyperpigmentation, granuloma formation, ulceration in the treated leg
- Thrombus formation in deep veins (e.g., femoral vein) in the treated leg
- Post-ablation superficial thrombus extension (PASTE) in the treated leg

8.2. Efficacy Assessments

8.2.1. Assessment of Symptoms

Efficacy assessment of patient improvement as compared to the baseline using the following scales at the post treatment follow up per [Table 3](#):

- VEINES-QOL/Sym Questionnaire (subset of Q1; i.e. five symptoms referred to as HASTI [Heaviness, Achiness, Swelling, Throbbing, Itching])
- Clinical-Etiology-Anatomy-Pathophysiology (CEAP) Classification
- European Quality of Life scale (EQ-5D-5L)
- Revised Venous Clinical Severity Score (rVCSS)
- Wong Baker Visual Analog Pain Scale (VAS)

8.2.2. Elimination of Saphenous Vein Reflux

Elimination of saphenous vein reflux at Week 12 post treatment, as demonstrated by duplex ultrasound based on vein closure and/or vein competency.

Vein Closure is defined as no discrete open segment of vein $> 5\text{cm}$ in length within the treatment section of the selected saphenous vein as assessed by duplex ultrasound.

Vein Competency is defined as absence of retrograde flow $> 500\text{ ms}$ (0.5 sec) within the treatment section of the selected saphenous vein as assessed by duplex ultrasound.

The endpoint is achieved when ultrasound images demonstrate vein closure and/or vein competency as read by an independent vascular core lab.

Refer to the [Appendix C](#) VICARES Clinical Study Procedure Manual for details.

8.2.3. Improvement in Patient Symptoms

Improvement in patient reported symptoms will be assessed at Week 12 post-treatment based on the responses to a subset of questions from VEINES-QOL/Sym questionnaire (an instrument of Varicose Vein Symptom Burden in patients with Superficial Venous); i.e., the 7-day average of five symptoms from Question 1 of the questionnaire referred to as HASTI symptoms (Heaviness, Achiness, Swelling, Throbbing, Itching).

The patient will record responses to HASTI symptom questions for 7 consecutive days at specific time points during the study as follows:

- For 7 days prior to the Day of Treatment
- For 7 days post Day of Treatment
- For 7 days, prior to Week 6 follow-up
- For 7 days, prior to Week 12 follow-up

,

9. WITHDRAWAL OF PATIENTS FROM THE STUDY

9.1. Prior to Randomization and Treatment

Individuals who withdraw from the study prior to randomization and treatment are not considered to be enrolled patients in the study, will not be used for assessment, and no follow up is necessary. Therefore, these individuals may be replaced.

9.2. Post Randomization and Treatment

Individuals who sign the Informed Consent and are randomized are considered enrolled patients and will be included in the Intent-To-Treat (ITT) analysis.

Possible reasons for withdrawal (discontinuation) of a patient from the study include:

Adverse Event (AE). An adverse event, which in the opinion of the Investigator, indicates that discontinuation from study would be in the best interest of the patient. Patient will be followed and treated by the Investigator until the abnormal parameter or symptom has resolved or stabilized. The reason for termination will be documented by the Investigator on the patient's source documents.

Patient withdrawal of consent (or assent). Patient may be withdrawn from the study at any time if the patient, the Investigator, or the Sponsor feels that it is not in the patient's best interest to continue. If the patient withdraws prior to completing the Week 12 Post Treatment Follow up Visit, patient is considered Lost-to-Follow up. In this event the Investigator should make at least two documented attempts to contact the patient and to have an early discontinuation visit. The reasons for patient withdrawal should be documented on the patient's source documents, if known.

Patient noncompliant with study procedures. If a patient is withdrawn prior to treatment due to lack of compliance with study procedures, the reason for withdrawal will be documented by the Investigator on the patient's source documents.

Sponsor requests early termination of study. If patient discontinuation (post randomization and treatment) is due to early termination of the study by the Sponsor, patient will be followed per the follow-up schedule to completion of the post-treatment Week 12 visit. The reason for termination will be documented by the Investigator on the patient's source documents.

10. SAFETY MONITORING DURING THE STUDY

10.1. Vital Signs

Vital signs will be taken at Visits 1 through Visit 6 (Screening through Week 12 post-treatment Visits). This should include temperature, pulse, respiratory rate, and blood pressure when patient is seated. Height and weight are required only at Screening Visit.

10.2. History/Varicose Vein History/Physical Examination

Medical and Vein history will be collected at the Screening (Visit 1). A physical examination will be performed and documented on the appropriate eCRF at Screening Visits.

10.3. Clinical Laboratory Safety Assessments

Hematological Assessments include: hemolysis, hematocrit, reticulocyte count, haptoglobins as described in [Section 8.1](#).

Intravascular coagulations include: Plasma fibrinogen level, Plasma D-dimer level platelet count, Prothrombin time (PT), Partial thromboplastin time (PTT) as described in Section 8.1. Plasma D-dimer level assessments will be conducted at: Baseline (Visit 2) immediately post Treatment (Visit 3) and at Week 1 follow-up (Visit 4); then, only at subsequent follow-up visits [Week 6 (Visit 5) and Week 12 (Visit 6)] if the D-dimer level is higher than it was at Baseline as described in [Section 8.1](#).

Other parameters and/or increased frequency of examinations may be needed, depending on the findings during the clinical study.

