7. VISIT SCHEDULE AND ASSESSMENTS

7.1. Study Visit Schedule and Assessments

A list of all study assessments is included in [Table 3](#), which indicates with an “X” if the assessment performed at that visit.

The Screening (Visit 1) evaluation should be performed \leq 30 days prior to Treatment (Visit 3). Additional screening will be performed at Baseline (Visit 2), not less than 7 days prior to Treatment (Visit 3).

Study visits, tests and/or procedures should occur on schedule per Table 3. Any exceptions will have to be approved by the sponsor.

Table 3: Visit Schedule and Assessments

Visit	Visit 1	Visit 2	Visit 3	Visit 4	Visit 5	Visit 6
	Screening Period		Treatment Period	Post-Treatment Follow-up Period		
	Screening	Baseline	Treatment	Week 1	Week 6	Week 12
Study Day(s)	-30 to -7	-10 to -7	Day 1	Day 7 (±2 days)	Day 42 (±5 days)	Day 84 (±7 days)
Informed Consent	X					
Inclusion/Exclusion criteria	X					
Medical History	X					
Diagnosis and Extent incompetent saphenous vein	X					
Demographics	X					
Physical Exam	X		X			
Pregnancy test (serum)		X				
Pregnancy test (urine)	X		X			
Height	X					
Weight	X					
Vital signs	X	X	X	X	X	X
Hematological Assessment ^a		X		X	X	X
Intravascular Coagulation Assessment ^{b, c}		X	X	X	X	X
Adverse events	X	Continuous				
Concomitant medications and Non-Drug procedures	X	Continuous				
Ultrasound	X	X	X	X	X	X
CEAP Classification	X					X
rVCSS	X					X
HASTI symptoms – 7-day assessment			X	X	X	X
European Quality of Life scale (EQ-5D-5L)		X	X	X	X	X
VEINES-QOL-SYM		X	X	X	X	X
VAS score		X	X (Procedure only)	X	X	X
ClariVein RES procedure			X			

^a Hematological Assessments include: Hemolysis, hematocrit, reticulocyte count, haptoglobins as described in [Section 8.1](#)

^b Intravascular coagulations include Plasma fibrinogen level, Plasma D-dimer level platelet count, Prothrombin time (PT), Partial thromboplastin time (PTT) as described in [Section 8.1](#).

^c Plasma D-dimer level assessments will be conducted at: Baseline (Visit 2) immediately post Treatment (Visit 3) and at Week 1 follow-up (Visit 4); then, only at subsequent follow-up visits [Week 6 (Visit 5) and Week 12 (Visit 6)] if the D-dimer level is higher than it was at Baseline.

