11. PLANNED STATISTICAL METHODS FOR ASSESSMENT OF EFFICACY AND SAFETY

11.1. General Considerations

Continuous variables will be summarized using descriptive statistics, specifically the mean, median, standard deviation, minimum and maximum. Categorical variables will be summarized using frequencies and percentages. All statistical tests will be performed at the 0.05 significance level (p -value ≤ 0.050) unless otherwise indicated.

For efficacy analyses, missing post-treatment data will be imputed using last observation carried forward (LOCF). Missing safety data will not be imputed.

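### D-dimer at Weeks 6 and 12 is collected only in patients above their own Baseline, so a change-from-baseline summary of those values would be biased upward

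*Combined protocol and SAP*

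**What the plan says.** D-dimer is part of the intravascular coagulation assessment in section 8.1. Under section 10.3 and footnote c of Table 3 it is measured in every patient at Baseline (Visit 2), immediately after treatment (Visit 3) and at Week 1 (Visit 4). At Weeks 6 and 12 it is measured only "if the D-dimer level is higher than it was at Baseline". Neither place says which earlier value is compared with Baseline: the immediate post-treatment value, the Week 1 value or the latest one. Section 10.3 refers to section 8.1, which lists the tests but does not contain the rule.

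On analysis, section 11.1 states "Continuous variables will be summarized using descriptive statistics, specifically the mean, median, standard deviation, minimum and maximum", and also "Missing safety data will not be imputed". Section 11.9 includes laboratory tests: "Safety will be assessed based on adverse events (including selected events of interest), clinical laboratory tests, physical examination, vital signs, and concomitant medications". It adds "Safety data will be summarized by treatment group and overall". By-visit and change layouts are given for one data type only: "Vitals signs data will be summarized by descriptive statistics for baseline, each post-treatment visit, and the change from baseline to each post-treatment visit". Physical examination data are explicitly to be listed without summaries, and laboratory data carry no such exemption. Section 11.9 rules out statistical testing of safety data.

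**The concern.** Whether a patient has a Week 6 or Week 12 value depends on that patient's D-dimer relative to Baseline. A patient whose Baseline was low by chance is more likely to be retested, and that same low Baseline is then subtracted to form the change. The retested group can therefore show a mean rise when nothing has changed.

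D-dimer is one of the plan's laboratory markers of intravascular coagulation after the sclerosant. Safety data are summarised by dose group, no safety test is planned, and section 12.4 provides for no Data Monitoring Committee. Readers will rely on the descriptive tables. A change table for this subset could suggest a persistent elevation that is partly or wholly produced by selection. It could also make the 1% and 3% arms look different because they were selected at different rates.

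**Working it through.** The plan gives no D-dimer figure to reproduce: no mean, SD, serial correlation or expected retest rate. The sizes below are in units of *s*, the within-patient SD at one visit, and rest on a stated model.

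**Inputs from the documents.** Everyone is measured at Baseline and Week 1; Weeks 6 and 12 are conditional (section 10.3, Table 3 footnote c). There is no imputation (section 11.1). There are 25 patients per arm (section 11.6).

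**Assumptions.** Each value is the patient's own level plus an independent normal error of SD *s*. There is no true change at Weeks 6 or 12. Retesting occurs if Week 1 (W1) exceeds Baseline (B). There may be a true transient Week 1 rise of *d* × *s*.

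**Formulas.** W1 − B is normal with mean *ds* and variance 2*s*².

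- Proportion retested = Φ(*d*/√2).
- Mean Week 6 change among the retested = (*s*/√2) × φ(*d*/√2) / Φ(*d*/√2).

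| True Week 1 rise *d* | Retested | Apparent mean change at Week 6 |
|---|---|---|
| 0 | 50% | 0.7071 × 0.3989/0.5000 = +0.56 *s* (= *s*/√π) |
| 1 | 76% | 0.7071 × 0.3107/0.7602 = +0.29 *s* |
| 2 | 92% | 0.7071 × 0.1468/0.9214 = +0.11 *s* |
| 3 | 98% | 0.7071 × 0.0420/0.9831 = +0.03 *s* |

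A simulation of 2,000,000 patients gave 0.561, 0.289, 0.112 and 0.030. With everyone measured, the mean change was 0.00 *s*.

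**Source of the bias.** With *d* = 0, the retested patients had a mean Baseline of −0.56 *s* relative to all patients, and a raw Week 6 mean of 0.00 *s*. The selection shifts the Baseline, not the Week 6 value.

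**Sensitivity to the reading of the trigger (*d* = 0).** If either the immediate post-treatment or the Week 1 value can trigger retesting, 67% are retested and the Week 6 change is +0.42 *s*. If Week 12 also requires Week 6 above Baseline, 33% are retested at Week 12 and the change is +0.84 *s*.

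**Sensitivity to serial correlation (*d* = 0).** With correlation of 0.3 or 0.6 between successive post-treatment errors, the Week 6 change is +0.73 or +0.90 *s*. The raw Week 6 mean of the retested then also rises, by +0.17 or +0.34 *s*.

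**Arms.** If one arm has a 1 SD transient rise and the other none, both being truly back at Baseline by Week 6, the apparent changes are +0.29 *s* and +0.56 *s*. The artefact is 0.56 − 0.29 = 0.27 *s*, and it favours the arm that truly rose.

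**Illustration of scale.** If *s* is 0.2 to 0.5 on the log scale (an assumption), +0.56 *s* corresponds to a ratio to Baseline of exp(0.2 × 0.564) = 1.12 to exp(0.5 × 0.564) = 1.33.

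**Counting untested patients as not above Baseline.** With *d* = 0, the proportion counted above at Week 6 is the probability that Baseline is the lowest of three exchangeable values, 1/3 = 33%. The true figure is 50%. In an arm with a 1 SD transient rise the simulation gives 44%, again against a true 50%. This count would create a spurious arm difference of 44 − 33 = 11 points.

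**The case against.** A reader might infer that the plan prescribes a biased D-dimer visit table. It does not. Section 11.9 gives by-visit and change layouts for vital signs alone, and laboratory tests are only to be summarised by group and overall. A D-dimer change table is a reasonable expectation from the general rule in section 11.1, not stated text.

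A reader might also infer that any Week 6 or Week 12 summary would show a rise with no true change. That is too strong. The raw mean of the retested patients, set against the all-patient Baseline mean, shows none when visit errors are independent. The upward bias belongs to the paired change.

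The size is also uncertain. The +0.56 SD figure assumes no real Week 1 response, and if most patients rise clearly after treatment the bias is close to nil. The arm artefact of 0.27 SD is small against sampling error: with about 12 and 19 patients retested (50% and 76% of 25), the standard error of that difference is about 0.48 SD.

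Finally, little formal inference depends on D-dimer. There is no safety testing, DVT and PASTE are assessed clinically and by ultrasound (section 10.5), and laboratory values are judged patient by patient (sections 10.7.1 and 10.10). The conditional rule can be read as follow-up of individual raised values.

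All of this stands and limits the point. It does not remove it: the values are collected selectively, they fall under a general instruction to report means, and nothing says how the selected subset is to be handled.

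**Conclusion.** The point holds in limited form. D-dimer at Weeks 6 and 12 will come from a group selected on the outcome, with no imputation and no stated rule for summarising it. A change-from-baseline summary of that group is biased upward: by +0.56 within-patient SD in the no-rise case, shrinking towards zero as the true Week 1 rise grows, and therefore by amounts that can differ between arms. These sizes rest on independent normal errors, a return to Baseline by Week 6 and Week 1 as the trigger. The documents supply no D-dimer data to test these assumptions and leave the trigger undefined. The consequence is confined to descriptive safety interpretation; no test or efficacy conclusion is affected. It is worth correcting because the correction is cheap.

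**What to change.** **Preferred.** Remove the condition in section 10.3 and in footnote c of Table 3, and run D-dimer for all patients at Weeks 6 and 12. Table 3 already schedules the coagulation assessment at both visits. The cost is at most two extra assays per patient, so at most 2 × 50 = 100 in the trial.

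**If the condition is kept:**

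- State which earlier value is compared with Baseline, for Week 6 and for Week 12.
- State in section 11.9 that mean changes from Baseline will not be presented for the retested subset.
- Report by arm the number tested and the number known to be above Baseline among those tested, with patients not retested by rule and missed visits as separate categories.
- Do not count untested patients as not above Baseline; as shown above, that understates the proportion and can create an arm difference.

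This alternative costs a few sentences and a table shell. Its limitation is that the count among those tested still describes a selected group. Under the same model it would be 0.333/0.500 = 67% in an arm with no rise and 0.443/0.760 = 58% in an arm with a 1 SD transient rise, when the true figure is 50% in both. It should be labelled as an account of what was observed, not as an estimate for the arm.
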